# 6.5 Duration of subject's expected participation in the entire trial

Each enrolled subject's participation in the trial will last approximately 12 months after randomization, following a two-week screening period prior to randomization (Visit 1).

# 6.6 Dose limiting toxicity (DLT)

During the time of enrollment into a given cohort, if any of the following events occur and are assessed to be vaccine related, further vaccination in that cohort will be suspended:

- Anaphylaxis reaction considered related;
- Generalized urticaria considered related;
- 1/3 trial subjects in that cohort with any severe unsolicited local reaction, if considered related and not manageable with simple measures (e.g. cooling, analgesia, nonsteroidal anti-inflammatory drugs [NSAID];
- Any possibly related AEs within 7 days of vaccination assessed to be potentially life-threatening (Grade 4);
- Any systemic SAE within 7 days of vaccination considered related;
- Any fever >40.0°C (>104.0°F) within 7 days of vaccination considered related;
- Occurrence of grade ≥3 adverse events that lasted at least 48 h and associated with vaccination, and for which there is no alternative feasible explanation, in more than 20% of participants (except local reactions: pain/tenderness, erythema/redness, and induration/swelling) after primary or booster inoculation;
- Occurrence of grade ≥3 clinical laboratory abnormality related adverse events with clinical manifestations, that not recovered for at least 8 days and associated with vaccination, and for which there is no alternative feasible explanation, in more than 20% of participants after primary or booster inoculation.

Approval from the SRC will be required prior to any further vaccination in the affected cohort. The SRC may call for the opening of a lower dose level cohort.

The same events will prompt IMP discontinuation for individual subjects as described in Section 6.9 until SRC review is completed.

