#### **Trial Design:**

This is a phase I, randomized, placebo-controlled, observer-blind, safety and immunogenicity study of SARS-CoV-2 mRNA vaccine (BNT162b1) in Chinese healthy subjects. After randomization, the trial for each subject will last for approximately 12 months. Screening period is 2 weeks prior to randomization (Day -14 to Day 0), and each dose of either SARS-CoV-2 vaccine (BNT162b1) or placebo will be given intramuscularly (IM) on Day 1 and on Day 22. After each age group completes the follow-up 28 days after boost vaccination (Day 50), initial analysis will be conducted.

Subjects who are  $\ge$ 18 years old and  $\le$  55 years old will be enrolled in adult group, and healthy elderly subjects who are  $\ge$ 65 years old and  $\le$ 85 years old will be enrolled in elderly group. Approximately 72 subjects for each age group will be allocated to three cohorts (BNT162b1 high-, low-dose groups and placebo group) in parallel, with approximately 24 subjects at each BNT162b1 dose level, including 24 placebo group subjects, the subjects will be randomized in a 1:1:1 ratio.

After the 14-day safety observation post the prime vaccination of the subjects in adult group, the prime vaccination for the subjects in the elderly group will start. SRC will review the available safety and tolerability data of all subjects in a cohort (including safety observation 14 days after the prime vaccination for all subjects in this cohort) before starting the boost vaccination for each cohort, to decide whether the BNT162b1 vaccine can be boosted.

For dose allocation design, see schematic diagram in **Figure 1**. For the planned assessments and visits, see schedule of activities in **Table 2**.

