- To date, there is very limited clinical experience with BNT162b1 vaccines in human subjects. Reactogenicity is anticipated and considered to contribute to the mode-of-action of inducing vaccine immune responses. Initial dose-ranging studies have suggested AE profiles consistent with previous usage of similar constructs in cancer patients, with AEs generally dividing into 2 groups: local injection site reactions and systemic flu-like illness. With BNT162b1 vaccines to date most reported AEs have been mild to moderate in intensity and no serious AEs have been reported. Fever of severe intensity has been reported. Most AEs can be managed with simple measures and resolve spontaneously. Short-lived effects can be seen on immune parameter due to the PD effects, such as lowering of lymphocytes due to temporary trafficking in to the lymph system, or raising of CRP. These are only regarded as AEs if there are clinical consequences.

The listed risks can be managed using routine symptom driven standard of care as described in Section 10.5. Treatment of these events is dependent on the discretion of the investigators.

The trial uses placebo control parallel design, to ensure trial subject safety during the trial. To further ensure trial subject safety, the trial protocol foresees that:

- They are much longer than used in recently completed FIH clinical trials investigating related RNA-based vaccines. For example, the two Moderna trials investigating mRNA vaccines against avian H10N8 and H7N9 influenza viruses in healthy adults that observed trial subjects on-site for only 1 h after each immunization before discharge from the trial site.
- More frequent on-site visits after immunization (i.e., on Days 2 and 8) than used in recently completed FIH clinical trials investigating with related RNA-based vaccines, e.g., the two Moderna trials investigating mRNA vaccines against avian H10N8 and H7N9 influenza viruses in healthy adults that used on-site visits on Day 8.
- Additional subject wellbeing calls may be included at the discretion of the SRC.
- In the case that an individual experiences dose limiting toxic events or that the frequency or pattern of AEs within a sub-cohort gives cause for concern, the investigator may request an ad hoc review by the SRC before further doses of a given vaccine construct are administered.

•

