# 6.2 Subjects enrollment and dose cohorts

The study will follow a parallel two-dose cohort and placebo design.

In the adult group, the enrollment process for subjects is as follows:

- In each planned low-dose cohort, high-dose cohort and placebo group, 72 subjects will be randomized in a 1:1:1 ratio to inject BNT162b1 or placebo vaccinated on Day 1.
- If the SRC considers that the subjects are safe with good tolerance after 14 days of observation, the boost vaccination will be conducted on Day 22.
- When the subjects in the adult group completed safety visits up to 14 days post prime vaccination, the available safety data for all subjects were summarized. If approved by the SRC,
  - o the planned dose cohort of elderly group will be initiated (see **Figure 1**). The data assessed by the SRC comprises: vital signs, TEAEs, local reactions, blood/clinical laboratory data and brief physical examination outcome.
  - o The parallel dose cohort study is conducted in the elderly group with consistent methods as those in the adult group (see **Figure 1**).

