## 6.7 Criteria for delay of boost vaccination and/or stop for boost vaccination

After enrollment, subjects may encounter clinical circumstances that warrant a delay in the administration of the subsequent vaccination of investigational vaccine/placebo. These situations are listed below:

- Individuals with a clinically significant active infection (as assessed by the investigator) or axillary temperature ≥37.3°C or oral temperature ≥38.0°C, within 3 days before intended investigational vaccine/placebo vaccination. Or other clinical symptoms/diseases that may be considered inappropriate for vaccination by the investigator
- Individuals who received any other vaccines within 21 days before planned vaccination.

If a subject meets a criterion for delay of vaccination, the subject may receive trial vaccination, if the subject is otherwise eligible for trial participation even if the window period of vaccination visit has passed. The decision to vaccinate in those situations will be taken by the investigator.

In this trial, the second vaccination may be stopped in some circumstances. These circumstances include systemic anaphylaxis or severe hypersensitivity reactions following the prime vaccine/placebo administration. If these reactions occur, the subject must not receive additional vaccinations; however, the subject is encouraged to continue in trial participation for safety reasons.

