# 6.8 Criteria for early study termination of a subject

Under some circumstances, a subject's trial participation may be terminated early. This means that no further trial procedures (including data collection) will be performed on that subject beyond the specific date of early termination. The primary reason for early termination of the subject from the trial should be recorded in the electronic Case Report Form (eCRF "end of study visit" page) using the following categories. For screen failure subjects, refer to Section 9.1.11.

- 1. Safety stopping criteria: The SRC will review and evaluate the collected safety data periodically during the trial. A decision to stop treatment for an individual subject or to terminate the trial may be taken if safety concerns are identified by the SRC. Suspected unexpected serious adverse reactions (SUSARs) will immediately be reviewed by the SRC. They will trigger a temporary stop of IMP administration to new subjects in the respective dose level cohort for that vaccine until the SRC recommendation to continue or to permanently stop IMP administration of new subjects in the respective dose level cohort for that vaccine.
- 2. Adverse events: the subject has experienced an AE (irrespective of being related to the trial vaccine or trial-related procedures) that requires early termination because continued participation imposes an unacceptable risk to the subject's health and / or the subject is unwilling to continue participation because of the AE. If the subject is unwilling to continue because of the AE the primary reason for early termination in this case will be 'withdrawal due to AE' and not 'withdrawal of consent', see below. Any ongoing AEs leading to early termination will be followed by the investigator until resolution or stabilization.
- 3. Lost to follow up: the subject did not return to the study site and several attempts to contact the subject were unsuccessful. Attempts to contact the subject must be documented.
- 4. Withdrawal of consent: the subject wishes to withdraw from the trial. The primary reason for early termination will be 'withdrawal of consent' if the subject withdraws from participation due to a non-medical reason (ie, reason other than AE). The reason for withdrawal, if provided, should be recorded in the eCRF.

Note: all attempts should be made to determine the underlying reason for the withdrawal and, where possible, the primary underlying reasons should be recorded.

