# 11.0 Monitoring Committee

# 11.1 Safety Review Committee (SRC)

Safety Review Committee (SRC) will be established comprising investigators, Fosun medical representatives, and medical monitor, etc.

Key roles of the SRC are as follows:

- Before progression to the next age group (elderly group), assess the safety and tolerability data of the subjects in the adult group completed safety visits up to 14 days after prime vaccination, and decide whether to approve initiation of the dose cohort of elderly group. Data collected include vital signs, TEAEs, local reactions, blood/clinical laboratory data, and brief physical examination outcome.
- Before each dose cohort begins boost vaccination, for each dose cohort, assess the safety and tolerability data of the prime vaccination of subjects (including data collected at least up to 14 days post-vaccination) and, decide whether to approve initiation of boost vaccination of this dose cohort. Data collected include vital signs, TEAEs, local reactions, blood/clinical laboratory data, and brief physical examination outcome.
- Throughout the trial, assess whether to replace trial subjects permanently discontinued due to safety issues.
- Throughout the trial, the SRC may specific additional dose levels to be tested and an appropriate regime for enrollment and safety oversight.

See SRC charter for more information. The SRC will act according to written procedures described in SRC charter.

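### The automatic cohort suspension in 6.6 is tied to enrollment, so read literally it lapses before boosting starts, contradicting two of its own triggers

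*Protocol*

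**What the plan says.** Protocol 6.6 lists eight events that suspend further vaccination in a cohort until the SRC approves a restart. The list opens with a time limit: "During the time of enrollment into a given cohort, if any of the following events occur and are assessed to be vaccine related". The last two items are frequency rules covering both doses; the final one applies when the abnormality occurs "in more than 20% of participants after primary or booster inoculation". SAP 4.1.3 repeats the opening and the list, but says vaccination is *stopped* where the protocol says *suspended*.

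The Trial Design part of the Trial Summary (2.0) fixes when boosting may begin. The SRC must first see the cohort's data, "including safety observation 14 days after the prime vaccination for all subjects in this cohort". Section 11.1 describes the SRC's task at that gate: to "assess the safety and tolerability data of the prime vaccination of subjects".

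Section 6.8 item 1 sends SUSARs to the SRC at once, and adds: "They will trigger a temporary stop of IMP administration to new subjects in the respective dose level cohort".

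Section 11.2 obliges the IDMC to review the safety data when DLT criteria are met, and leaves the pause to its judgment. Under 4.3.1, "the investigator may request an ad hoc review by the SRC before further doses of a given vaccine construct are administered".

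**The concern.** The rule that stops vaccination without waiting for a committee is switched on by enrollment. If enrollment into a cohort is over before anyone in it is boosted, the rule is off for the whole boost phase, although its authors wrote two triggers for events after the booster.

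Suppose one of the first subjects boosted at 30 µg has related anaphylaxis. Site staff need to know whether the next subject may be injected. The opening of 6.6 suggests that they may, while the booster triggers suggest that the suspension was meant to apply. Section 6.8 does not resolve this, because the subjects waiting for a boost are not new. What is at stake is the exposure of already primed subjects in the interval before a committee decides.

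**Working it through.** **The plan's own figure.** Section 13.3 gives an 86.5% chance of at least one TEAE in 24 subjects at a rate of 8%. This reproduces: 1 − 0.92^24 = 0.865. It plays no part in this point, which rests on reading the sections together and on the visit calendar.

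**Step 1: when enrollment closes.** Inputs from Table 2: Visit 4 on Day 15 ±1, so v = 13 to 15 days after prime; Visit 5 (boost) on Day 22 ±2. Put the cohort's first prime on calendar day 1, its last prime on day E and its first boost on day B (20 to 24). The gate needs the last subject's Visit 4 before the first boost:

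E + v ≤ B, so E ≤ B − v.

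| First boost, day B | Latest E, v = 13 | Latest E, v = 14 | Latest E, v = 15 |
|---|---|---|---|
| 20 | 7 | 6 | 5 |
| 22 | 9 | 8 | 7 |
| 24 | 11 | 10 | 9 |

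The gap B − E is at least v, that is, at least 13 to 15 days. No planned boost falls inside the period named in 6.6.

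**Step 2: is the cohort perhaps a dose arm pooled over both age groups?** Then enrollment would still be open when adults are boosted. But the gate uses the same word and would become unworkable. Elderly priming waits for the adults' 14-day observation. Even if every adult is primed on day 1 and every visit is a day early, elderly priming starts on day 14 and the elderly 14-day data arrive on day 14 + 13 = 27. The adult boost window closes on day 24. Section 13.3 also treats dose cohorts as belonging to an age group.

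**Step 3: which triggers are affected.** Two of the eight name the booster. Each needs more than 20% of participants: 4/24 = 16.7% and 5/24 = 20.8%, so at least 5 of 24. On the literal reading their booster half can never operate. Five others act on a single case (anaphylaxis, generalized urticaria, a Grade 4 event, a systemic SAE, fever above 40.0 °C). These are where an immediate hold matters most, and they lapse too.

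**Step 4: what else acts after an event in a boosted subject.**

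| Provision | Mandatory? | Does it hold the other subjects' boosts? |
|---|---|---|
| SRC gate (2.0, 11.1) | Yes | No; it precedes boosting and uses prime-dose data |
| Individual holds (6.6 last sentence, 6.7, 6.9) | 6.6 and 6.7: yes; 6.9: by criterion | No; they act on the affected subject, who has no dose left |
| SUSAR stop (6.8) | Yes | No; new subjects only |
| SRC review of a SUSAR (6.8) | Yes | Only if the SRC so decides |
| IDMC review of a DLT (11.2) | Yes | Only if the IDMC so decides |
| Ad hoc SRC review (4.3.1) | No | Only if requested and so decided |

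**Step 5: would a hold have time to act?** The documents do not give the pace of priming. If it takes 8 days, first boosts fall on day 22 and nominal boosts run to day 8 + 21 = 29. If it takes 10 days, the first boost is on day 24 and the last nominal one on day 31. Either way boosting spreads over about a week. After an event in the first boosted subject, up to 24 − 1 = 23 in that cohort may still be waiting. If the whole cohort were primed on one day, little time would remain.

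**The case against.** The best defense is that 6.6 was plainly meant to reach the boost. Two triggers say so, restart approval covers any further dose in the cohort, and 6.2 sets out the Day 22 boost under the words "In the adult group, the enrollment process for subjects is as follows". Against that, 6.7 opens its rules on the second dose with "After enrollment, subjects may encounter clinical circumstances that warrant a delay in the administration of the subsequent vaccination". Section 6.7 speaks of an individual's status, so it does not settle when enrollment into a cohort closes. What stands is that the text supports two readings.

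A reader might go further and infer that no mandatory safeguard covers the boost phase. The documents do not support that. SRC review of SUSARs and IDMC review of DLT events are obligatory with no enrollment limit, no cohort is boosted without SRC approval, and 6.7 bars a second dose after systemic anaphylaxis or severe hypersensitivity to the first. The gap is narrower: nothing automatic holds the cohort while the committees deliberate.

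A reader might also size the gap from the US data in 4.2.4.1, where fever of at least 38.0 °C at 30 µg rose from 1/12 after dose 1 to 9/12 after dose 2. That is not a 6.6 event; the trigger is above 40.0 °C. The same summary reports no Grade 4 systemic event or fever and no serious adverse event, and 4.2.4 calls reactions after the two doses similar. The documents give no rate for the 6.6 events, so the chance of a second one cannot be estimated from them.

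Two further limits stand. The SRC and IDMC charters are not among the documents and may require a pause. Replacement of discontinued subjects (11.1) could also reopen enrollment.

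**Conclusion.** The point holds as an internal contradiction in a stopping rule. The opening of 6.6 and SAP 4.1.3 ends the automatic suspension at least 13 to 15 days before a cohort's first boost, while two of the eight triggers presuppose that it still runs. Read literally, a related anaphylaxis or Grade 4 event in a boosted subject requires review but no pause, and up to 23 further boosts in the cohort are permitted meanwhile. The SUSAR stop has the same gap for primed subjects awaiting boost.

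This rests on three assumptions: enrollment ends when the last subject is randomized and primed, no replacements are enrolled, and the charters add no pause. The calendar result is an inference from the SRC gate and is not stated in the plan. It is worth amending because site staff must be able to act on the protocol text. No sample size or analysis result changes.

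**What to change.** - **Protocol 6.6 and SAP 4.1.3:** replace the opening time limit with *At any time from the first prime vaccination to the last boost vaccination in a cohort*. Leave the eight events and the individual hold at the end of protocol 6.6 unchanged.
- **SAP 4.1.3:** change *stopped* to *suspended*, to match the protocol.
- **Protocol 6.8 item 1:** make the temporary stop, and the SRC recommendation that ends it, cover all remaining prime and boost doses in the affected dose cohort.

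This is a short text amendment with notice to sites, and needs no new visits or data items. It has two costs. A hold may push some boosts past Day 22 ±2 and move the bleeds that follow. Section 6.7 already allows late boosts for individual reasons, but the blinded data review should state how boosts delayed by a hold count for the per protocol set. Because allocation is blinded, a hold on one dose cohort must be run through the IRT and unblinded staff, or be applied to the whole age group.

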## 6.7 Criteria for delay of boost vaccination and/or stop for boost vaccination

After enrollment, subjects may encounter clinical circumstances that warrant a delay in the administration of the subsequent vaccination of investigational vaccine/placebo. These situations are listed below:

- Individuals with a clinically significant active infection (as assessed by the investigator) or axillary temperature ≥37.3°C or oral temperature ≥38.0°C, within 3 days before intended investigational vaccine/placebo vaccination. Or other clinical symptoms/diseases that may be considered inappropriate for vaccination by the investigator
- Individuals who received any other vaccines within 21 days before planned vaccination.

If a subject meets a criterion for delay of vaccination, the subject may receive trial vaccination, if the subject is otherwise eligible for trial participation even if the window period of vaccination visit has passed. The decision to vaccinate in those situations will be taken by the investigator.

In this trial, the second vaccination may be stopped in some circumstances. These circumstances include systemic anaphylaxis or severe hypersensitivity reactions following the prime vaccine/placebo administration. If these reactions occur, the subject must not receive additional vaccinations; however, the subject is encouraged to continue in trial participation for safety reasons.

# 6.8 Criteria for early study termination of a subject

Under some circumstances, a subject's trial participation may be terminated early. This means that no further trial procedures (including data collection) will be performed on that subject beyond the specific date of early termination. The primary reason for early termination of the subject from the trial should be recorded in the electronic Case Report Form (eCRF "end of study visit" page) using the following categories. For screen failure subjects, refer to Section 9.1.11.

- 1. Safety stopping criteria: The SRC will review and evaluate the collected safety data periodically during the trial. A decision to stop treatment for an individual subject or to terminate the trial may be taken if safety concerns are identified by the SRC. Suspected unexpected serious adverse reactions (SUSARs) will immediately be reviewed by the SRC. They will trigger a temporary stop of IMP administration to new subjects in the respective dose level cohort for that vaccine until the SRC recommendation to continue or to permanently stop IMP administration of new subjects in the respective dose level cohort for that vaccine.
- 2. Adverse events: the subject has experienced an AE (irrespective of being related to the trial vaccine or trial-related procedures) that requires early termination because continued participation imposes an unacceptable risk to the subject's health and / or the subject is unwilling to continue participation because of the AE. If the subject is unwilling to continue because of the AE the primary reason for early termination in this case will be 'withdrawal due to AE' and not 'withdrawal of consent', see below. Any ongoing AEs leading to early termination will be followed by the investigator until resolution or stabilization.
- 3. Lost to follow up: the subject did not return to the study site and several attempts to contact the subject were unsuccessful. Attempts to contact the subject must be documented.
- 4. Withdrawal of consent: the subject wishes to withdraw from the trial. The primary reason for early termination will be 'withdrawal of consent' if the subject withdraws from participation due to a non-medical reason (ie, reason other than AE). The reason for withdrawal, if provided, should be recorded in the eCRF.

Note: all attempts should be made to determine the underlying reason for the withdrawal and, where possible, the primary underlying reasons should be recorded.

- 5. Premature study termination by Fosun, a regulatory agency, the IEC/IRB, or any other authority. If the clinical study is early terminated by the Fosun, the investigator is to promptly inform the subjects and local EC/IRB and should assure appropriate follow up for the subjects. The primary reason for early termination in this case will be 'trial termination'.
- 6. Subject's death during trial participation.
- 7. Other.

Note: the specific reasons should be recorded in the "specify" field of the eCRF.

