## **5.2.2** Secondary endpoints

Safety and tolerability of BNT162b1, as determined by:

- The proportion of subjects experiencing SAEs, occurring up to Day 21 after prime vaccination and Day 28 after boost vaccination, up to Month 3, 6 and 12.
- The proportion of subjects experiencing AE associated with BNT162b1, occurring up to Month 3, 6 and 12.
- The proportion of of subjects experiencing abnormal markers of hematology, blood chemistry and urine analysis, occurring at Hour 24 and Day 7 after prime vaccination and Day 7 period after boost dose of BNT162b1 or placebo.

*Immunogenicity of BNT162b1, as determined by:* 

- Geometric mean titer (GMT) of anti-S1 IgG antibody at Day 7, Day 21 after prime vaccination, at Day 7, Day 21 after boost vaccination, and at Month 3, 6 and 12.
- Geometric mean titer (GMT) of anti-RBD IgG antibody at Day 7, Day 21 after prime vaccination, at Day 7, Day 21 after boost vaccination, and at Month 3, 6 and 12.
- GMT of SARS-CoV-2 neutralizing antibody (including true virus-based SARS-CoV-2 neutralizing test) at Day 7, Day 21 after prime vaccination, at Day 7, Day 21 after boost vaccination, and at Month 3, 6 and 12.
- Fold increase in antibody anti-S1 IgG antibody titers, as compared to baseline, at Day 7, Day 21 after prime vaccination, at Day 7, Day 21 after boost vaccination, and at Month 3, 6 and 12.
- Fold increase in antibody anti-RBD IgG antibody titers, as compared to baseline, at Day 7, Day 21 after prime vaccination, at Day 7, Day 21 after boost vaccination, and at Month 3, 6 and 12.
- Fold increase in SARS-CoV-2 neutralizing antibody titers (virus neutralizing test), as compared to baseline, at Day 7, Day 21 after prime vaccination, at Day 7, Day 21 after boost vaccination, and at Month 3, 6 and 12.
- Seroconversion rates (SCR) defined as a minimum of 4-fold increase of antibody titers, as compared to baseline, at Day 7, Day 21 after prime vaccination, and at Day 7, Day 21 after boost vaccination.

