# 6.9 Criteria for premature discontinuation of trial vaccine application

Early (premature) study termination of a subject will by default prevent the subject from continued Trial Vaccine administration, as the subject will no longer be participating in the study.

In addition to early termination (see Section 6.8) criteria, other situations may apply in which subjects may continue participating in the trial (eg, contributing safety data according to protocol) but Trial Vaccine application is discontinued selectively. Regardless of the reasons for discontinuation of Trial Vaccine application, this must be documented as protocol deviation. Even if the subject is deemed ineligible to continue to receive Trial Vaccine, all efforts should be made to continue the collection of safety data according to protocol. In addition, the one primary reason for early discontinuation of Trial Vaccine application should be recorded in the eCRF, "end of Trial Vaccine application" page using the following categories.

- 1. Adverse events: the subject has experienced an AE (irrespective of being related to the Trial Vaccine or trial-related procedures) for which subsequent Trial Vaccine applications impose an unacceptable risk to the subject's health, but the subject will continue trial participation or other study procedures for safety.
- 2. Lost to follow up: the subject did not return to the clinical and several attempts to contact the subject were unsuccessful. Attempts to contact the subject must be documented
- 3. Withdrawal of consent: the subject wishes to withdraw from the trial. The primary reason for early termination will be 'withdrawal of consent' if the subject withdraws from participation due to a non-medical reason (ie, reason other than AE). The reason for withdrawal, if provided, should be recorded in the eCRF.
- 4. Premature study termination by Fosun, a regulatory agency, the IEC/IRB, or any other authority. If the clinical study is early terminated by the Fosun, the investigator is to promptly inform the study subjects and local EC/IRB and should assure appropriate follow up for the subjects. The primary reason for early termination in this case will be 'trial termination'.
- 5. Subject's death during trial participation.

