# 9.3.6 Follow-up extension

The extension visits will be performed at Visit 10 (Month 3), Visit 11 (Month 6), and at Month 12 (Visit 12). If a subject terminates earlier, a final Visit procedure should be performed, if possible.

The following procedures will be performed:

- 1. Collect travel history (to SARS-CoV-2 endemic countries and SARS-CoV-2 endemic regions of China) and concomitant medications/vaccinations (see Section 9.1.2).
- 2. Perform symptom-directed physical examination (if deemed necessary, see Section 9.1.4).
- 3. Check vital signs (see Section 9.1.5).
- 4. Collect blood sample for immunogenicity assessment (see Section 9.1.6.5).

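### Protocol 6.8 stops collection of new safety events at early termination and lists an SRC treatment stop as a termination reason, whereas 6.9 keeps collecting safety data after a vaccine stop

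*Protocol*

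**What the plan says.** Protocol 6.8 defines early termination of a subject as the point after which "no further trial procedures (including data collection) will be performed on that subject beyond the specific date of early termination". It then lists the reasons to be recorded. Item 1, on safety stopping, includes "A decision to stop treatment for an individual subject" by the SRC. Item 2 covers an AE that makes continued participation unacceptable or that the subject will not continue with, and adds: "Any ongoing AEs leading to early termination will be followed by the investigator until resolution or stabilization". Withdrawal of consent for non-medical reasons is a separate item.

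Protocol 6.9 covers subjects who stop the vaccine but may stay in the trial. For them "all efforts should be made to continue the collection of safety data according to protocol". Protocol 6.7, on stopping the boost after a severe allergic reaction, says "the subject is encouraged to continue in trial participation for safety reasons".

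Protocol 9.3.6, on the Month 3, 6 and 12 visits, says: "If a subject terminates earlier, a final Visit procedure should be performed, if possible". Its procedure list has travel history, medication, examination, vital signs and blood sampling, but no AE recording. Table 2 does mark AE recording at Visits 10, 11 and 12 for both age groups.

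The first secondary safety endpoint in Protocol 5.2.2 is the proportion of subjects with SAEs, "occurring up to Day 21 after prime vaccination and Day 28 after boost vaccination, up to Month 3, 6 and 12". The second is the proportion with vaccine-related AEs up to Months 3, 6 and 12.

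**The concern.** Two things are at stake. The first is consistency: the follow-up of a subject whose vaccination the SRC has stopped should not depend on which eCRF page the site completes.

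The second is informative loss. In a trial whose primary objective is safety, subjects who leave for safety reasons are the ones whose later course matters most. If events that begin after exit are not collected, and the analysis still counts those subjects in the denominator, the long-term SAE and related-AE proportions can be too low for reasons connected with tolerability itself.

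**Working it through.** **1. The plan's own figure.** Protocol 13.3 and SAP 4.3 give 24 subjects per dose group and an 86.5% chance of seeing at least one TEAE at a true rate of 8%. Check: 1 − 0.92^24 = 0.8648, so the figure reproduces and is not in dispute. If 1, 2, 3 or 4 of the 24 were not observed at all, the chance would be 85.3%, 84.0%, 82.6% or 81.1%. That overstates any loss here, because subjects who leave are observed until they leave. The sample-size rationale is not threatened. The issue lies in the follow-up endpoints.

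**2. What is collected after an exit for safety.**
- The AE that caused the exit, if ongoing: followed (6.8 item 2).
- SAEs and related AEs still present when collection ends: followed (10.4).
- An SAE, AESI or vaccine-related AE that first appears after exit: covered by neither provision, and excluded by the general sentence in 6.8.

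Protocol 10.2.2 asks for related events later than 28 days after the boost, and 4.3.1 promises safety monitoring to about 12 months after the last immunization. Neither says that it overrides 6.8 for a subject who has left.

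**3. Where an SRC treatment stop is recorded.** Protocol 6.6 sends an individual with a dose-limiting event to 6.9, but only while the SRC's review is pending. If the SRC then makes the stop permanent, the one category that names an SRC decision is 6.8 item 1, which ends data collection. Section 6.9 has no SRC category, though its AE or 'other' entry could be used. The same decision therefore has two possible homes with opposite consequences.

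**4. What the SAP does with the gap.** The Safety Set is everyone dosed (SAP 6). Percentages use the analysis set as denominator (SAP 7.1.1). Missing data are not handled (SAP 7.9). A subject with no recorded event stays in the denominator as a non-event to Month 12.

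**5. Which exits can lose an endpoint event.** The endpoints count subjects with at least one event, cumulatively. Hence:
- Exit because of a related SAE: already counted for both endpoints, so nothing is lost.
- Exit because of a non-serious related AE: counted for related AEs; a later first SAE would be missed.
- Exit because of an unrelated SAE: counted for SAEs; a later first related AE would be missed.
- Exit because of a non-serious unrelated AE, or an SRC stop in a subject with no counted event: either could be missed.

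**6. Size per missed event.** In one dose group of one age group, 1/24 = 4.2 percentage points. If it is the only event, 1/24 (exact 95% CI 0.1% to 21.1%) becomes 0/24 (0% to 14.2%). In the pooled-age analysis of SAP 7.8, the group has 24 + 24 = 48 subjects and the loss is 1/48 = 2.1 points. A subject who leaves at Day 22 misses 366 − 22 = 344 days of follow-up to the Month 12 visit.

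**The case against.** Several stronger readings are tempting, and the documents do not support them.

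A reader might infer that 6.8 ends all data collection for anyone leaving because of an AE. It does not: item 2 and 10.4 keep the exit event and other persisting SAEs or related AEs under follow-up. The loss is confined to new events and scheduled assessments.

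A reader might also see a contradiction between the AE categories of 6.8 and 6.9. These are separate dispositions: one ends participation and the other stops the vaccine only, and 6.9 presents itself as additional to 6.8. Nor is 6.7 directly contradicted, since stopping the boost there does not trigger 6.8. Only the SRC clause in 6.8 item 1 overlaps.

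The final visit in 9.3.6 need not conflict with 6.8, because a visit on the termination date is not beyond it. The missing AE entry in 9.3.6 is largely editorial, because Table 2 schedules AE recording at Visits 10 to 12.

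On bias, subjects whose exit event already counts for an endpoint remain in its numerator, so it would be wrong to say that the most harmed subjects disappear from the results. The trial is descriptive, and SAP 7.2 and 7.6.1 already report discontinuations by reason, follow-up completion and TEAEs leading to discontinuation.

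All of this narrows the point, and two things survive it. The SRC clause still conflicts with 6.9, and no provision captures new events after exit. Discontinuation tables show how many left, but not how many were under observation at each safety time point or what happened to them afterwards.

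**Conclusion.** The concern holds in limited form. Protocol 6.8 item 1 and 6.9 give opposite follow-up for the same SRC decision, and the data-collection sentence in 6.8 leaves new SAEs, AESIs and vaccine-related AEs uncollected after a safety exit, while two secondary endpoints run to Month 12.

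The per-event sizes in the working assume that the subject had no event already counted for that endpoint, then had a first qualifying event after leaving, and that the SAP's denominator rule is applied as written. The documents give no rate of safety exits and no rate of later events. The expected bias therefore cannot be stated, and neither can the claim that it falls most heavily on one arm. It may be zero in a trial of this size. The point is worth correcting because the rule is written down, the affected subjects are selected by tolerability, and the correction is cheap.

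**What to change.** - Reconcile 6.8 item 1 with 6.9 on what follow-up applies after an SRC decision to stop an individual's treatment. This review takes no position on which stopping rule is right.
- Reword the data-collection sentence in 6.8 so that subjects who leave for safety reasons and still consent to contact have new SAEs, AESIs and vaccine-related AEs collected at the Month 3, 6 and 12 time points. A telephone call is enough. Collection would still end at death, loss to follow-up, withdrawal of consent to further data collection, or termination of the whole trial.
- Align the 9.3.6 procedure list with Table 2 by adding AE recording.
- In the SAP, show by group the number of subjects still under observation at each follow-up safety time point.

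Cost: protocol and SAP wording, one added row in the follow-up safety tables, and at most three calls for each affected subject. Vaccination, randomization and sample size do not change.
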